8.3 Continued Treatment beyond Progression of Disease

Accumulating evidence indicates a minority of patients treated with immunotherapy may derive clinical benefit from continued treatment despite initial evidence of progressive disease.⁶⁷ For this reason, patients will be permitted to continue study therapy beyond initial investigator-assessed RECIST 1.1-defined progression as long as they meet the 2 criteria listed below.

- Investigator-assessed clinical benefit, and
- Subject is tolerating study drug

The assessment of clinical benefit should take into account whether the subject is clinically deteriorating and unlikely to receive further benefit from continued treatment.

All decisions to continue treatment beyond initial progression must be discussed with the MDACC IND Office and documented in the study records.

Patients should discontinue study therapy upon evidence of further progression, defined as an additional 10% or greater increase in tumor burden from time of initial progression (including all target lesions and new measurable lesions).

New lesions are considered measurable at the time of initial progression if the longest diameter is at least 10 mm (except for pathological lymph nodes, which must have a short axis of at least 15 mm). Any new lesion considered non-measurable at the time of initial progression may become measurable and therefore included in the tumor burden measurement if the longest diameter increases to at least 10 mm (except for pathological lymph nodes, which must have an increase in short axis to at least 15 mm).

For statistical analyses that include the investigator-assessed progression date, patients who continue treatment beyond initial investigator-assessed RECIST 1.1-defined progression will be considered to have investigator-assessed progressive disease at the time of the initial progression event.

9.0 PRE-TREATMENT EVALUATION

9.1 Within 28 days of study entry

- Signed and dated informed consent.
- Physical Exam and updated medical history
- Updated evaluation of concurrent non-malignant diseases and recent medical therapy (within the thirty days prior to the evaluation).
- Imaging: CT scan of chest, abdomen, and pelvis (MRI of abdomen and pelvis may substitute CT abdomen/pelvis). CT scan or MRI of the brain.
- Plain films of bones/skeletal survey and bone scan will be ordered only if clinically indicated
- 12-lead ECG

9.2 Within 14 days (+/- 3 days) of study entry

- Confirmation of the eligibility of patients (see Section 4 for detailed Inclusion/Exclusion criteria)
- Histologic diagnosis/confirmation of RCC with clear cell component
- Baseline signs and symptoms
- Current medications
- Interim history
- Assessment of Karnofsky performance status, weight, temperature, blood pressure, heart rate, respiratory rate, oxygen (O_2) saturation
- Physical Examination
- Laboratory testing:
 - CBC with differential & platelets
 - Chemistry panel including electrolytes (Na, K, Cl, CO_2), albumin, alkaline phosphatase, ALT, AST, calcium, LDH, total bilirubin, BUN, creatinine, Phosphorus
 - INR/PTT
 - Lipid profile
 - Blood glucose
 - Serum amylase and lipase,
 - Serum free T4 and TSH.
 - Serum ACTH and Cortisol
 - Blood samples for Immune Testing and Correlative Studies
 - Urinalysis: Gross examination including specific gravity, protein, glucose, and blood; microscopic examination including white blood cells / high power field (WBC/HPF), red blood cells / high power field (RBC/HPF) and any additional findings.
 - If urine protein ≥ 100 mg/dL then obtain random urine protein/creatinine ratio
 - Serum or urine pregnancy test for females of childbearing potential
- Collect fresh biopsy (optional / up to 14 days prior)
- Complete e-tablet QOL assessments (FACT, SF-12, CES-D, Social Provisions Scale, FMCS, History of Depression)

9.3 Within 6 months (180 days) of study entry

- Doppler echocardiogram

9.4 Treatment can not start until at least 1 week after any minor surgical procedure, excluding placement of a vascular access device and core biopsies.

10.0 EVALUATION DURING TREATMENT

- 10.1 A cycle of treatment is defined as 2 weeks (+/- 3 days), or 4 weeks +/- 3 days if the

Proprietary of MD Anderson Cancer Center

patient is switched to the nivolumab schedule of 480 mg IV every 4 weeks. The following must be performed on Day 1 of each course. If assessment and tests were completed within 7 days of Course 1 Day 1, procedures will not be repeated. Patients are required to come to MD Anderson at the beginning of every course.

- Interim history
- Assessment of Karnofsky performance status, weight, temperature, blood pressure, heart rate.
- Physical examination
- Assessment of all concomitant medications and treatments taken since the last assessment. Concurrent medications related to co-morbidity (e.g. hypertension, diabetes, etc.) will be recorded in the database. The name, dose, date start and stop (as accurately as possible) along with indication of the medication will be collected.
- Assessment of adverse events and tumor-related signs and symptoms
- Assessment of treatment related toxicities
- Laboratory testing:
 - CBC with differential & platelets
 - Chemistry panel including electrolytes (Na, K, Cl, CO₂), alkaline phosphatase, ALT, AST, calcium, total bilirubin, BUN, creatinine
 - Blood for correlative studies
 - Tissue sample

10.2 After 2 weeks (\pm 3 days) of MGCD516 monotherapy: collect blood samples as well as optional fresh biopsy for immune testing and correlative studies to assess treatment response to MGCD516 monotherapy.

10.3 The following labs will additionally be obtained at 6 weeks (42 days +/- 3 days), 12 weeks (84 days +/- 7 days), and every 12 weeks (84 days +/- 7 days) for as long as patients are receiving therapy on protocol :

- Lipids
- Blood glucose
- Serum amylase and lipase
- Serum free T4 and TSH.
- Serum ACTH and Cortisol
- Chemistry panel including electrolytes (Na, K, Cl, CO₂), albumin, alkaline phosphatase, ALT, AST, calcium, LDH, total bilirubin, BUN, creatinine, phosphorus
- Urinalysis: Gross examination including specific gravity, protein, glucose, and blood; microscopic examination including white blood cells / high power field (WBC/HPF), red blood cells / high power field (RBC/HPF) and any additional findings.
 - If urine protein \geq 100 mg/dL then obtain random urine protein/creatinine ratio.
- Optional: on the 4th week (\pm 3 days) of therapy on protocol (following at least 1 infusion of nivolumab): collect blood samples for immune testing and correlative studies to assess treatment response to combination therapy.

Proprietary of MD Anderson Cancer Center

10.4 Imaging scans (CT of chest and CT scan or MRI of abdomen/pelvis) will be performed to determine disease response at 6 weeks (42 days)(+/- 3 days), 12 weeks (84 days +/- 7 days), and every 12 weeks (84 days +/- 7 days), for as long as patients are receiving therapy on protocol. A follow-up CT or MRI of the brain will only be ordered if clinically indicated.

10.5 Echocardiogram will be obtained on the 12th week (\pm 14 days) of therapy on protocol and then repeat every 6 months (\pm 1 month) or as clinically indicated.

10.6 Complete e-tablet QOL assessments (FACT, SF-12, CES-D, FMCS) at 2 weeks (\pm 7 days), 6 weeks (\pm 7 days), 12 weeks (\pm 7 days) and every 12 weeks (\pm 7 days) thereafter.

10.7 End of Treatment Evaluation: Adverse events and tumor-related signs and symptoms will be assessed. For patients who develop toxicity related to study drug necessitating discontinuation of protocol therapy before restaging to assess tumor response, physicians treating these patients will make every effort to repeat the appropriate imaging studies if feasible and indicated to assess tumor response at the time the patients are taken off protocol treatment. For patients taken off protocol therapy due to disease progression, blood samples and tumor biopsy (optional at the physician's discretion) will be collected within 28 days from the time that disease progression is first confirmed and used for immune testing and correlative studies.

10.8 Long-term Follow-Up: Patients will be followed for survival every 3 months (90 days \pm 1 month or 28 days) by record review or telephone correspondence. Patients in long term follow up at the time of Long Term Extension Phase approval will be assessed for survival every 6 months (180 days +/- 1 month or 28 days)

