7.0 CORRELATIVE STUDIES

We will perform immune monitoring, including but not limited to the evaluation of CD4 and CD8 T cells in available tumor tissue and peripheral blood samples as previously published.⁶³⁻⁶⁶ Peripheral blood and tumor tissue samples (optional) will be obtained within 14 days pretreatment, 2 weeks after MGCD516 monotherapy, following 2 infusions of Nivolumab, and upon disease progression. All samples will be collected and analyzed per a separate IRB-approved protocol. In addition, another IRB-approved protocol, separate from the aforementioned immunotherapy analyses, will be used to investigate in the blood and tumor tissues, a panel of cytokines, chemokines, cell-free DNA, and other relevant angiogenic factors, biological receptors, ligands, nucleotides and proteins.

Up to one hundred (150) ml of blood will be drawn at the visits outlined in Sections 9 and 10. These samples will be labeled with confidential identification numbers and provided to the Immunotherapy platform for immunological assessments. A detailed laboratory manual highlighting the blood collection and processing procedures will be prepared. All blood collection will be compliant with institutional safety standards and will not exceed the maximum blood draw per venipuncture policy.

Blood and tissue collections for correlative studies will not be performed during the long term extension phase of the trial. The only exception is optional collection of blood or tissue samples for those patients taken off therapy due to disease progression to assess causes of disease progression.

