- l. After 2 weeks (\pm 3 days) of MGCD516 monotherapy: collect fresh biopsy (optional at the physician's discretion) to assess treatment response to MGCD516 monotherapy
- m. Within 28 days of study entry
- n. Within 14 days (+/- 3 days) of study entry
- o. If urine protein \geq 100 mg/dL on urinalysis then obtain random urine protein/creatinine ratio
- p. Patients will continue to receive MGCD516 daily until disease progression or unacceptable treatment-related toxicity
- q. Patients will receive nivolumab as a 60 \pm 15 minute IV infusion on Day 1 of a treatment cycle every 2 weeks until disease progression or intolerance. Patients may be dosed no less than 12 days from the previous dose. Patients who have received at least 6 infusions of nivolumab 240 mg IV every 2 weeks with no DLTs related to nivolumab, will have the option to transition to the equivalent nivolumab schedule of 480 mg IV every 4 weeks.
- r. On the 4th week (\pm 3 days) of therapy on protocol (following at least 1 infusion of nivolumab): collect blood sample (optional at the physician's discretion) for correlative studies to assess treatment response to combination therapy
- s. On the 6th week (\pm 3 days) of therapy on protocol (following at least 2 infusions of nivolumab): collect blood sample for correlative studies to assess treatment response to combination therapy
- t. On the 6th week (\pm 3 days) of therapy on protocol (following at least 2 infusions of nivolumab): collect fresh biopsy (optional at the physician's discretion) to assess treatment response to combination therapy
- u. Obtain an echocardiogram on the 12th week (\pm 14 days) of therapy on protocol and then repeat every 6 months (\pm 1 month)
- v. In patients taken off therapy due to disease progression, collect blood sample for correlative studies to assess causes of disease progression
- w. In patients taken off therapy due to disease progression, collect fresh biopsy (optional at the physician's discretion) to assess causes of disease progression.
- x. Complete e-tablet QOL assessments (FACT, SF-12, CES-D, Social Provisions Scale, FMCS, History of Depression) within 14 days (+/- 7 days) of study entry
- y. Complete e-tablet QOL assessments (FACT, SF-12, CES-D, FMCS) at 2 weeks (\pm 7 days), , 6 weeks (\pm 7 days), 12 weeks (\pm 7 days) and every 12 weeks (\pm 7 days) thereafter

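### Section 10.1 requires correlative blood and a tissue sample on Day 1 of every course, contradicting Section 7, the rest of Sections 9 and 10 and the study calendar, where biopsies are optional and both collections are limited to a few time points

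*Combined protocol and SAP*

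**What the plan says.** Section 10.1 governs what happens at the start of each course: "The following must be performed on Day 1 of each course". Under laboratory testing, the list ends with "Blood for correlative studies" and "Tissue sample". The only relief is for Course 1, where items completed within the preceding 7 days need not be repeated. On course length the section says "A cycle of treatment is defined as 2 weeks (+/- 3 days"), lengthening to 4 weeks if the "patient is switched to the nivolumab schedule of 480 mg IV every 4 weeks".

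Section 7 describes a much shorter programme. Samples "will be obtained within 14 days pretreatment, 2 weeks after MGCD516 monotherapy, following 2 infusions of Nivolumab, and upon disease progression", with tissue marked optional. It then adds: "Up to one hundred (150) ml of blood will be drawn at the visits outlined in Sections 9 and 10".

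The other numbered sections follow the shorter programme. Section 9.2 makes the baseline biopsy optional, 10.2 does the same at the end of the 2-week monotherapy period, 10.3 offers an optional week-4 blood sample, and 10.7 makes the biopsy at progression optional.

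The study calendar places the blood and tissue rows in its block of optional procedures and leaves the each-cycle column blank for both. Every tissue footnote (i, l, t, w) says optional. Footnote t, for week 6, reads: "collect fresh biopsy (optional at the physician's discretion) to assess treatment response to combination therapy".

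**The concern.** A site working from 10.1 and a site working from the calendar would run different sampling programmes, and the documents give no rule on which one governs. Section 7 adds to the difficulty by sending the reader to Sections 9 and 10 for the blood-draw visits, which brings in the 10.1 list.

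Two things are at stake. The first is burden: a required invasive sample at each course is a different request to patients from a few optional biopsies. The second is the record: if staff follow the calendar, a monitor reading 10.1 could log a missed procedure at courses where none was intended, and it becomes unclear which biomarker samples were planned. Biomarkers of treatment response are a secondary objective, so the planned time points should be unambiguous.

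**Working it through.** No statistical formula applies. The check sets the passages side by side and counts the collections that each implies.

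**1. Side by side**

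| Place | Tissue | Correlative blood |
|---|---|---|
| 10.1 | Day 1 of every course, no optional label | Day 1 of every course, no optional label |
| 7 | four time points, optional | the same four time points |
| 9.2 | baseline, optional | baseline |
| 10.2 | Day 15, optional | Day 15 |
| 10.3 | none | week 4, optional |
| 10.7 | progression, optional | progression |
| Calendar | pre-study, Day 15, week 6, progression; all optional | pre-study, Day 15, week 4, week 6, every 12 weeks, progression |

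Day 15 is Day 1 of Course 2. On that one day 10.1 requires tissue and 10.2 makes it optional, so the conflict lies inside Section 10 itself.

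The table shows two further gaps. Apart from the 10.1 item, no numbered line in Section 10 covers the week-6 correlative blood and biopsy (footnotes s and t) or the every-12-week correlative blood. For blood, Section 7 has four time points and the calendar six.

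**2. Collections under 10.1 by Day 85**

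Course Day 1s fall on 1 + 14 × (k − 1), giving Days 1, 15, 29, 43, 57, 71 and 85, which is 7. If the Course 1 exemption applies, 7 − 1 = 6.

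The move to 4-week cycles needs at least 6 two-weekly infusions. The first is on Day 15, so the sixth is on Day 85 and the earliest 4-weekly dose is on Day 99. The 2-week interval therefore holds throughout this window.

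**3. Collections in the calendar over the same window**

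- Tissue: pre-study, Day 15, week 6 = 3, all optional.
- Blood: pre-study, Day 15, week 4, week 6, week 12 = 5.

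These counts include pre-study. Counting only on-treatment collections, the calendar has 3 − 1 = 2 biopsies and 5 − 1 = 4 blood sets, against 6 or 7 of each under 10.1.

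**4. Longer horizon**

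Assume 48 weeks (336 days) on treatment, about 11 months. Section 3.4 reports a posterior mean of 11.7 months for median PFS.

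- No switch: 48 / 2 = 24 courses.
- Earliest switch: 7 courses through Day 85, then Day 1s at 99, 127, …, 323, which is (323 − 99) / 28 + 1 = 9. Total 7 + 9 = 16.

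The range is 16 to 24 tissue samples, one fewer at each end if the Course 1 exemption applies.

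**5. Blood volume**

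Section 7 gives the ceiling in words as one hundred and in figures as 150 ml. At that ceiling, 7 draws come to 700 or 1,050 ml and 6 draws to 600 or 900 ml. The calendar's 5 come to 500 or 750 ml. These are upper limits, not expected volumes.

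**The case against.** The strongest reply is that nobody would read 10.1 as ordering a biopsy every 2 weeks. It says tissue sample, under laboratory testing; every other passage on biopsy makes it optional; and 10.2, which follows directly, would be pointless if 10.1 already required one. This looks like a leftover list item, and that stands. It explains the contradiction without removing it, since the operative word in 10.1 is mandatory.

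Section 7 also says that sampling runs under a separate IRB-approved protocol with a laboratory manual, so the working schedule may sit in documents not available here. That is fair, and it limits what can be said about actual practice.

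Three stronger inferences are tempting and are not supported:

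- **That the week-6 combination sample is missing from the protocol.** It appears in Section 7 (after two nivolumab infusions) and in footnotes s and t. The calendar stands between 10.9 and Section 11, so Section 7's pointer can be read as reaching it. Only a numbered Section 10 line is lacking.
- **That the draws would harm patients admitted with hemoglobin of 9 g/dl.** The volume is a ceiling, Section 7 binds collection to institutional safety standards and a per-venipuncture maximum, and the documents give no basis for deriving a hemoglobin effect.
- **That nearly every course has been a deviation.** The documents do not show how sites classified missed samples.

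The prospective reach is also limited. Section 3.4 reports 42 patients enrolled through February 2020, with 12 still on treatment at the September 2020 cutoff. Section 7 ends correlative collection in the extension phase except for optional samples at progression.

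**Conclusion.** The inconsistency is real. Taken literally, 10.1 calls for 6 or 7 tissue and blood collections by Day 85, against 3 optional biopsies and 5 blood sets in the calendar, and for roughly 16 to 24 tissue samples over 48 weeks. The longer-run figure rests on the assumed time on treatment and on whether and when the patient moves to 4-week cycles.

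It is most likely a drafting error in 10.1, because the other passages agree that biopsies are optional and few. It should still be corrected, since an operative rule contradicts the rest of the protocol and no stated precedence resolves it. The consequences are for patient burden, deviation classification and the record of planned biomarker samples. The dose-finding endpoints and the sample size are not affected.

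**What to change.** 1. Delete the correlative-blood and tissue items from the 10.1 per-course list.
2. Add a Section 10 line for week 6 (± 3 days) covering correlative blood and the optional biopsy, matching footnotes s and t.
3. Add a Section 10 line for the every-12-week correlative blood. Without it, deleting the 10.1 item would leave that draw with no numbered line.
4. Align Section 7's time points with the calendar's, and point its blood-volume sentence to the calendar's correlative time points instead of to Sections 9 and 10 in general.
5. Reconcile the blood volume so that words and figure agree. The documents do not show which is intended, so the sponsor must confirm it.

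The cost is amendment wording. No time point in Section 7 or the calendar is lost, the stated burden falls, and no dose, endpoint or analysis changes. The separate sampling protocol and the laboratory manual should be checked against the corrected schedule.

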10.9 Long term Extension Phase
Upon analysis of primary endpoints, the Investigator, sponsor and supporter may agree to notify patients of the status of the clinical trial and allow patients on study medication if they agree and consent. The supporter will continue to supply the MGCD516 (sitravatinib) drug until the treating physician determines to withdraw study medication due to adverse events progression or patient decision.
Data collection will include visit date, assessment of compliance per patient statement, preferable with a medication recorded on study calendar. Patients who choose not to record doses on a medication calendar will not constitute a deviation or violation of the protocol. Patients will be asked to return to MD Anderson every 2 to 3 months (8 to 12 weeks) for resupply of study medication. The return appointment timing is at the discretion of the treating physician. MGCD516 will not be mailed except when acts of nature make it impossible to travel, such as hurricanes, other natural storms (such as snowstorms) or in the case of manmade disasters such as fire. Patients may remain on MGCD516 even if nivolumab is withdrawn. As the nivolumab is per standard of care dose and schedule the infusions may be scheduled locally with the instruction of a local physician letter ("dear doctor" letter). Serious adverse events will be reported and assessed by the MD Anderson study team.

Proprietary of MD Anderson Cancer Center

STUDY CALENDAR

	Pre-Study	Day +1	Day+15 (C2D1)	Each 14 or 28 day cycle (+/- 3 days) ^z	4 weeks (28 days)(+/- 3 days) from day+1	6 weeks (42 days)(+/- 3 days) from day+1	Every 12 weeks (84 days +/- 7 days)	End of treatment
Informed Consent	X ^m							
Confirmation of eligibility	X ⁿ							
Histologic diagnosis/confirmation	X							
Medical History	X ^m							
Interim History	X ⁿ			X		X	X	X
Physical Examination	X ⁿ			X		X	X	X
Imaging	X ^{b,m}					X ^b	X ^b	X ^j
Echocardiogram	X ^a							X ^u
Weight, temperature, blood pressure, heart rate and respiratory rate	X ⁿ			X ^h		X	X	
O2 saturation	X ⁿ							
CBC with differential & platelets	X ^{c,n}			X ^c		X ^c	X ^c	
Chemistry Panel	X ^{d,n}			X ^g		X ^d	X ^d	
INR/PTT	X ^{d,n}							
Serum Free T4 + TSH	X ⁿ					X	X	
Serum ACTH and	X ⁿ					X	X	
Urinalysis	X ^{n,o}					X ^o	X ^o	
Pregnancy Test	X ^{n,f}							
Lipid Profile	X ⁿ					X	X	
Blood glucose	X ⁿ					X	X	
Amylase and Lipase	X ⁿ					X	X	
12-Lead ECG	X ^m							
Karnofsky Performance Status	X ⁿ			X		X	X	X
Concomitant Medications	X ⁿ			X		X	X	X
Adverse Events				X		X	X	X
Initiate daily oral MGCD516		X ^p						
Initiate IV nivolumab			X ^q					
QOL assessment	X ^{n,x}		X ^y			X ^y	X ^y	
Long Term Follow Up								X ^k
Optional Procedures								
Blood for correlative studies	X ⁿ		X ^e		X ^r	X ^s	X	X ^v
Tissue Sample	X ^{n,i}		X ^l			X ^t		X ^w

a. During Pre-Study, must be within six months of study entry.

Proprietary of MD Anderson Cancer Center

- b. CT scan of chest, CT scan or MRI of abdomen/pelvis at 6 weeks (42 days)(+/- 3 days) from study day 1, then every 12 weeks (84 days)(+/- 7 days) after day 1. CT scan or MRI of the brain only at baseline (within 28 days of study entry), and can be repeated if clinically indicated. Plain films of bones/skeletal survey and bone scan will not be ordered routinely on all patients but only if clinically indicated; any follow-up CT scan or MRI will be ordered if clinically indicated.
- c. Differentials include neutrophils, lymphocytes, monocytes, eosinophils and basophils
- d. Includes electrolytes (Na, K, Cl, Co2), albumin, alkaline phosphatase, ALT, AST, calcium, LDH, total bilirubin, BUN, creatinine, phosphorus, glucose, INR/PTT (pre-study only)
- e. After 2 weeks (\pm 3 days) of MGCD516 monotherapy: collect blood sample for correlative studies to assess treatment response to MGCD516 monotherapy
- f. Only for women of childbearing potential. May be serum or urine.
- g. Only includes electrolytes (Na, K, Cl, Co2), alkaline phosphatase, ALT, AST, calcium, total bilirubin, BUN, and creatinine
- h. Only blood pressure and heart rate
- i. Optional fresh biopsy at the physician's discretion (up to 14 days prior)
- j. For patients who develop toxicity related to study drug necessitating discontinuation of protocol therapy before restaging to assess tumor response, physicians treating these patients will make every effort to repeat the appropriate imaging studies if feasible and indicated to assess tumor response at the time the patients are taken off protocol treatment.
- k. Patients will be followed for survival every 3 months (90 days \pm 1 month or 28 days) by record review or telephone correspondence. Patients in long term follow up at the time of Long Term Extension Phase approval will be assessed for survival every 6 months (180 days \pm 1 month or 28 days)
- l. After 2 weeks (\pm 3 days) of MGCD516 monotherapy: collect fresh biopsy (optional at the physician's discretion) to assess treatment response to MGCD516 monotherapy
- m. Within 28 days of study entry
- n. Within 14 days (+/- 3 days) of study entry
- o. If urine protein \geq 100 mg/dL on urinalysis then obtain random urine protein/creatinine ratio
- p. Patients will continue to receive MGCD516 daily until disease progression or unacceptable treatment-related toxicity
- q. Patients will receive nivolumab as a 60 \pm 15 minute IV infusion on Day 1 of a treatment cycle every 2 weeks until disease progression or intolerance. Patients may be dosed no less than 12 days from the previous dose. Patients who have received at least 6 infusions of nivolumab 240 mg IV every 2 weeks with no DLTs related to nivolumab, will have the option to transition to the equivalent nivolumab schedule of 480 mg IV every 4 weeks.
- r. On the 4th week (\pm 3 days) of therapy on protocol (following at least 1 infusion of nivolumab): collect blood sample (optional at the physician's discretion) for correlative studies to assess treatment response to combination therapy
- s. On the 6th week (\pm 3 days) of therapy on protocol (following at least 2 infusions of nivolumab): collect blood sample for correlative studies to assess treatment response to combination therapy
- t. On the 6th week (\pm 3 days) of therapy on protocol (following at least 2 infusions of nivolumab): collect fresh biopsy (optional at the physician's discretion) to assess treatment response to combination therapy
- u. Obtain an echocardiogram on the 12th week (\pm 14 days) of therapy on protocol and then repeat every 6 months (\pm 1 month)
- v. In patients taken off therapy due to disease progression, collect blood sample for correlative studies to assess causes of disease progression
- w. In patients taken off therapy due to disease progression, collect fresh biopsy (optional at the physician's discretion) to assess causes of disease progression.
- x. Complete e-tablet QOL assessments (FACT, SF-12, CES-D, Social Provisions Scale, FMCS, History of Depression) within 14 days (+/- 7 days) of study entry
- y. Complete e-tablet QOL assessments (FACT, SF-12, CES-D, FMCS) at 2 weeks (\pm 7 days), , 6 weeks (\pm 7 days), 12 weeks (\pm 7 days) and every 12 weeks (\pm 7 days) thereafter
- z. patients who switch to nivolumab 480mg will, from that time onwards, have physical exam, CBC and chemistry panel every 4 weeks (28 days \pm 3 days) instead of every 2 weeks (14 days \pm 3 days)

Long Term Extension Phase Schedule of Events

Event	Every 8 to 12 weeks (56 to 84 days +/- 7 days)	End of treatment Plus 30 days post last dose
Follow up exam with physician or delegated advance practice provider	X	X
Assessment of serious adverse events	X	X
Disease assessment per the discretion of the treating physician	X	X
daily oral MGCD516		
IV nivolumab *every 4 weeks per standard of care	X*	X
Routine laboratory assessment per the discretion of the treating physician		
Blood and tissue for correlative studies		X ^a

^a In patients taken off therapy due to disease progression, collect optional blood and tissue sample for correlative studies to assess causes of disease progression

